### **1.3 Procedures for tDCS with svPPA Sub-Study**

After obtaining informed consent, a baseline language assessment will be performed twice, on separate days, for all subjects, regardless of whether they will be assigned to sham or real tDCS stimulation first. Depending on the subject, this assessment is expected to take 1-2 hours. Performance will be audio-recorded. The assessment will include the following measures:

- Global Cognition: we will administer the Montreal Cognitive Assessment, a commonly used measure of cognitive abilities.
- Semantic Memory: Pyramid and Palm trees: a well-standardized test in which subjects see 3 pictures or words on a page and are asked which two "go together"; for example on one

page, the pictures include a drawing of a glove, hand and foot.

- Category fluency: a series of tasks in which subjects are asked to generate as many words as possible in one minute that are members of a specific category; semantic categories will include tools, animals, and vegetables.
- Executive Processing: The Digit Symbol task from the Wechsler Adult Intelligence scale will be administered to test sustained attention and executive ability. Subjects will also be asked to generate words starting with the letters F, A and S.
- Naming: The Peabody Picture Vocabulary Test (PPVT-IV) and the Philadelphia Naming Test (PNT) will be administered, both commonly used tests to assess naming and general language ability.

Half of subjects will undergo 10 sessions of sham stimulation first and will then undergo 10 sessions of real tDCS stimulation. Half of subjects will undergo 10 sessions of real tDCS stimulation first and will then undergo 10 sessions of sham stimulation. A complete language assessment will be performed before stimulation sessions, after the 10th stimulation session, and 12 weeks and 6 months ( $\pm$  1 week) after the completion of stimulation sessions. Real tDCS stimulation will be administered using the Soterix 1x1 using a current of 2 mA. The cathodal current will be split across two electrodes (5cm^2) positioned over the left and right temporal regions respectively. The anodal electrode (5x7cm) will be placed over the forehead. During sham stimulation, a 2 mA current will be delivered for approximately 10 seconds at the beginning of the sham condition before being extinguished over the course of seconds. After the first 10 minutes of stimulation, in both real and sham conditions, participants will begin the behavioral treatment, which will continue for 45 minutes; therefore there will be 20 minutes of concurrent tDCS and behavioral therapy.

Prior to initiating treatment, we will craft an individualized training lexicon for each patient. This training vocabulary contains familiar people, household items, foods, activities, cloths, and hygiene implements. Target words are represented by photographs of the patient's own items. We will employ several item-level controls to examine treatment generalization. The first will test the impact of personal familiarity by asking patients to name and generate features for canonical rather than personal photographs. The second condition will evaluate within-category generalization by asking patients to name and generate features for their own untrained items. The final item-level comparison will examine generalization of naming accuracy to untrained

exemplars from the Philadelphia Naming Test. Once an item pool is established, baseline naming accuracy and eye-tracking measures will be acquired. During baseline testing sessions, we will identify target items as either known or vulnerable based on their consistency of being named. We will isolate vulnerable versus mastered items for each patient and apply different training for each. Vulnerable items will be treated using a modified semantic feature analysis approach. Mastered items will be trained using cued picture naming. Assignment of a particular target item to either treatment condition is dynamic. Once a vulnerable target item has been mastered, it will move to the mastery list. Similarly, mastered items later forgotten can move to the vulnerable list. Each treatment session will include pretest/post-test naming probes for vulnerable items. Mastery item lists will be probed once weekly.

Following the pretest, a clinician will train all of a patient's vulnerable target items in completely randomized order. Training proceeds by positioning the target photograph in the center of a blank feature matrix. The clinician then announces the target item's semantic features. After this modeling procedure, the clinician cues the patient to name the target picture, generate its features, and name it again. The same item will be present repeatedly until the patient can successfully generate the target image's name and >50% of its features. The clinician will then proceed to the next item, continually cycling through the list for 45 to 60 minutes. In addition to intensive semantic training on vulnerable items, patients will train on naming their mastery items, albeit less frequently and less comprehensively. Mastery list training involves random presentation of the target pictures with cues to name each. No clinician feedback is given, and the final response is scored for accuracy.

Safety and tolerability of the treatment will be assessed in several manners. First, the inclusion/exclusion screening form will be administered both at the initial intake session, as well as at the first session of each 2-week stimulation block. Second, subjects will be queried about new symptoms or adverse effects prior to stimulation on all days when stimulation will be given; should subjects have any concerns, tDCS will not be performed and language will be assessed with fluency tests, naming and a speech sample will be elicited. Third, in the absence of symptoms, language will be assessed at the end of one week of treatment with picture naming, fluency measures and a speech sample will be elicited. Should performance be significantly worse than prior to initiation of treatment, the study will be discontinued; in this event, subjects will be followed

on a weekly basis for 4 weeks or until performance returns to baseline (whichever comes first). We propose to use a "significant" change in performance as a cut-off because performance in this condition in the absence of any intervention is quite variable.

## **2. Statistical Analysis**

Data from each subject will be analyzed using a within-subject design in which change in performance from the baseline testing session to the post-therapy (0, 6, 12 weeks post tDCS) will be compared using t-tests, ANOVAs and other univariate statistics. As it is most relevant to real-world behavior, elicited speech production will serve as the primary endpoint. Depending on our ability to recruit a reasonable sample, group analyses will be also be performed. Finally, we note that high quality imaging will be available for the majority of subjects. Note that we are not proposing to obtain imaging under the auspices of the present study; this data will be available from [name] previously cited protocol. We will perform exploratory analyses in which we attempt to determine if specific imaging parameters (e.g., cortical thickness, degree of atrophy) predict response to tDCS.

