## **2. Accrual**

There is no information on the basis of which to determine the appropriate sample size. All subjects with Primary Progressive Aphasia who meet Inclusion and Exclusion criteria will be invited to participate.

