#### ***2.1 Design of tDCS-Only Study***

This is a sham-controlled, full cross-over study design. All subjects with PPA will participate in ten 20-minute tDCS stimulation sessions over the course of 2 weeks using 1.5 mA current. A battery of language tasks will be administered before stimulation sessions, after the 10 sessions, and again at 6 and 12 weeks after the stimulation sessions. The 12-week follow up session will serve as the "baseline" session for the following stimulation sessions. All subjects will also participate in ten 20-minute sham stimulation sessions over the course of 2 weeks. During sham tDCS, a 1.5 mA current will be delivered for approximately 30 seconds at the beginning of the sham session before being extinguished over the course of seconds. Participants will be randomly assigned to receive sham or tDCS stimulation first.

For example, a subject who is assigned to sham stimulation sessions first will first undergo baseline language testing. Then the subject will participate in ten 20-minute sham stimulation sessions over the course of 2 weeks. The subject will go through follow up language testing after the 10th sham stimulation sessions as well as 6 and 12 weeks following the sham stimulation sessions. The 12 week follow up session will serve as the "baseline" for the tDCS stimulation sessions, after which the subject will participate in ten 20-minute tDCS stimulation sessions over the course of 2 weeks, using 1.5 mA current.

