#### ***2.2 Design for HD-tDCS+CILT Sub-study***

For the HD-tDCS+CILT study, we will use the same sham-controlled, full cross-over design described above, with two exceptions: 1) We will conduct two baseline testing sessions on separate days prior to the start of the 10-day tDCS block, to facilitate screening for CILT and to ensure a stable estimate of language performance at baseline; 2) After the completion of the final 12-week follow-up visit, participants will have the option to undergo an additional 10-day round of “booster” HD-tDCS/sham+CILT. This booster will be open to any patients as an optional incentive for patients whose completion of the study coincided with perceived benefits from the combined therapy. The booster will involve the same time-course of language assessments, HD-tDCS+CILT sessions, and follow-up testing out to 12 weeks after the final HD-tDCS session. This optional third arm of the protocol will thus be identical to the real HD-tDCS arm in all ways (i.e., assessment schedule, subject compensation, tDCS parameters etc.) except that participants may opt in or out as they see fit. In other words, all participants are expected to complete the first two arms of HD-tDCS/sham stimulation; then, those who have completed all the scheduled study visits may choose to undergo a third round, during which we will continue to collect the same data that we have collected throughout the rest of the study.

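### The analysis plan defaults to each subject's own data, makes the group analysis conditional on recruitment with no threshold, and never states the active-versus-sham contrast that the crossover randomises

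*Combined protocol and SAP*

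**What the plan says.** The whole analysis plan is one paragraph, Study Procedures, 2. Statistical Analysis. Its default is "Data from each subject will be analyzed using a within-subject design". The quantity is "change in performance from the baseline testing session to the post-therapy (0, 6, 12 weeks post tDCS"), and these changes "will be compared using t-tests, ANOVAs and other univariate statistics". It adds that "elicited speech production will serve as the primary endpoint", and then: "Depending on our ability to recruit a reasonable sample, group analyses will be also be performed". It gives no number, date or decision-maker for what counts as reasonable. It also states no significance level, model, unit of replication, error term or comparison of active with sham.

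The Accrual section offers nothing to fill the gap: "There is no information on the basis of which to determine the appropriate sample size". The Study Duration sections for tDCS-Only and HD-tDCS+CILT forecast about 10 subjects a year for about 2 years.

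The three Design sections (tDCS-Only, HD-tDCS+CILT, svPPA) each describe a sham-controlled full crossover with assignment to sham first or active first. In tDCS-Only the last follow-up of the first block is also the baseline of the second.

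**The concern.** The group analyses are something done in addition, so the opening sentence most naturally describes an analysis of one person at a time. Two problems follow.

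First, the only analysis that uses the randomised order and can speak about patients with PPA in general is the one made optional. A test inside one person has no between-subject error term. However small its p-value, it concerns that person only, whereas the objective in section 1.1 concerns patients with PPA. A before-after change within a block also mixes any stimulation effect with practice, placebo response and disease progression. The sham block is there to remove these.

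Second, if the within-person test is a t-test on the three changes from baseline, those changes are not independent replicates. All three subtract the same baseline score, and the error in that score never reaches the standard error.

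**Working it through.** The plan states no error rate, SD or powered sample size, so there is no figure of its own to reproduce.

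**Inputs.** Three follow-ups per block (0, 6, 12 weeks), k = 3, and one baseline session, b = 1 (Statistical Analysis; tDCS-Only design). Ten sessions over 2 weeks put the visits at about weeks 0, 2, 8 and 14. Assumed, because not stated: two-sided 5% level, equal visit-error variance s², no effect, no drift.

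**Independent errors.**
- Change at follow-up j: d_j = y_j − y_0.
- True variance of the mean change: s²/3 + s² = 4s²/3.
- Variance the t-test estimates: y_0 cancels from the spread of the three d_j, leaving s²/3.
- Ratio 4, so t is inflated by √4 = 2.
- Critical value on 2 df is 4.303, so the actual rate is P(|t₂| > 4.303/2 = 2.151).
- For 2 df, P(|t| > x) = 1 − x/√(2 + x²) = 1 − 2.151/√6.628 = **0.164**.

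**Serial correlation.** Take correlation r per 6 weeks, decaying with the time between visits. At r = 0.5:
- The baseline's correlations with the three follow-ups are 0.794, 0.397 and 0.198 (sum 1.389). Those among the follow-ups are 0.5, 0.5 and 0.25 (sum 1.25).
- True variance of the mean change: s²[1 + (3 + 2×1.25)/9 − 2×1.389/3] = 0.685s².
- Estimated variance: s²(1 − 1.25/3)/3 = 0.194s². Ratio about 3.5.
- The visits are no longer interchangeable, so the rate is taken from simulation (400,000 replicates): **12.0%, 11.4% and 10.9%** at r = 0.3, 0.5 and 0.7.

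**How far this depends on the test chosen.** With independent errors the inflation factor is √(1 + k/b).

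| Within-subject test | Type I error |
|---|---|
| Changes, 1 baseline, 3 follow-ups | 16.4% |
| Changes, mean of 2 baselines, 3 follow-ups | 11.3% |
| Changes, 1 baseline, 2 follow-ups | 8.6% |
| Changes, mean of 2 baselines, 2 follow-ups | 7.1% |
| Raw scores, 1 baseline against 3 follow-ups, pooled variance | 5.0% |

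The two-baseline rows matter because HD-tDCS+CILT says "We will conduct two baseline testing sessions on separate days prior to the start of the 10-day tDCS block", and svPPA procedures also test baseline twice. The two-follow-up rows match the svPPA Design section after its first block. At the protocol's visit times with r = 0.3-0.7, the raw-score test gives about 3%.

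**Scale.** With about 10 × 2 = 20 subjects, each tested once at 16.4%, 20 × 0.164 = 3.3 false positives are expected, against 20 × 0.05 = 1. The chance of at least one is 1 − 0.836²⁰ = 97%. It is already 1 − 0.95²⁰ = 64% at a true 5%.

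**Does a group analysis cure it?** One active-minus-sham change contrast per subject, tested by a paired t-test across subjects, was simulated with the 12-week visit re-used as second baseline and no carryover or period effect. Type I error was 5.1% at N = 10 and 5.0% at N = 20. For 80% power the standardised paired effect must be about 1.00 at N = 10 and 0.66 at N = 20.

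**The case against.** The opening sentence can be read differently. A within-subject design is also the ordinary name for a repeated-measures analysis across subjects, the designs are randomised crossovers, and relating imaging to response needs several subjects. On that reading, though, the separate sentence on group analyses is hard to explain, and the recruitment condition and missing sham contrast remain. The per-person reading is the more natural one, but not certain.

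A stronger objection is that no specific test is stated. A reader might infer that the plan's tests carry an error rate of 11-24%. The documents do not support that. The level is an assumption, and a pooled raw-score test that fits the same sentence runs at about 3-5%. The upper figure needs a per-person active-versus-sham t-test that the section never mentions; with independent errors and the re-used 12-week baseline, such a test would be at about 28%, not 24%. Nor does the plan say that visits are the replicates. Items could be, for example the 60 naming pictures in HD-tDCS+CILT, which raises a different dependence problem. This objection stands, so the inflation can only be stated conditionally.

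A reader might also infer repeated looks at the group result, or a headline list of individual responders. The documents describe neither, and the condition concerns recruitment, not results.

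**Conclusion.** The concern holds, with moderate confidence because the opening sentence is ambiguous. The firm part needs no arithmetic: the group analysis is conditional without a threshold, no active-versus-sham contrast is stated, and single-subject tests cannot carry the population-level objective.

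The numerical part is conditional. For a t-test on three changes from one baseline, at an assumed two-sided 5% level with no effect and no drift, the false-positive rate is about 16% with independent errors. It is about 11-12% with correlation 0.3-0.7 per 6 weeks at the protocol's visit times. It is smaller with two baselines or two follow-ups under independent errors, and absent for the pooled raw-score test under the assumptions checked.

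**What to change.** In Study Procedures, 2. Statistical Analysis:

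- Delete the clause that makes group analyses depend on recruitment.
- For each of the three studies separately, make the primary analysis one active-minus-sham change contrast per subject from the two randomised blocks. Compare it across all randomised subjects, with subject as the unit and allowance for period and sequence.
- Name the endpoint and follow-up time for each study from what its own battery and schedule collect in both blocks. Elicited speech fits tDCS-Only, with one of its several scores named. It is not listed in the HD-tDCS+CILT or svPPA baseline batteries, so those need another endpoint.
- Run the analysis once, after the last enrolled subject finishes, whatever number was recruited.
- For small numbers, use a re-randomisation test that follows the actual allocation scheme. With unrestricted 4:4 or 5:5 allocation the smallest two-sided p is 2/70 = 0.029 or 2/252 = 0.008. svPPA is stratified by Montreal Cognitive Assessment performance: two strata of 2:2, for example, give 6 × 6 = 36 allocations and a smallest p of 2/36 = 0.056.
- Report single-subject results descriptively, as plots without p-values.

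The cost is wording only: no added visits, procedures or subjects. The downside is that individual significant results can no longer be claimed. Correctly specified single-subject inference is a legitimate alternative in a rare disorder, but it would need its own model and could not replace the group comparison.

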**PROTOCOL ABSTRACT**

The purpose of this study is to treat the language impairment of subjects with Primary Progressive Aphasia using transcranial direct current stimulation (tDCS) and high definition transcranial direct current stimulation (HD-tDCS). PPA is a slowly progressive impairment in language that may be observed in patients with neurodegenerative conditions such as Fronto-temporal dementia or, less commonly, Alzheimer's Disease. tDCS is a form of non-invasive brain stimulation in which very small current (here, 1.5 mA) is applied to the scalp. tDCS will be administered in ten 20 minute sessions over the course of two weeks. Language function will be assessed before, after 1 week of treatment, after 2 weeks of treatment and at 6 and 12 weeks after completion of tDCS. In a sub-study under this protocol, we will pair HD-tDCS with Constraint-Induced Language Therapy (CILT), which preliminary evidence has shown may be a useful speech therapy for individuals with PPA. In this sub-study, we will investigate whether HD-tDCS can enhance the potential benefits of speech therapy (usually very modest in PPA).

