## **2. Primary Outcome Variable(s)**

Outcomes will be assessed with a variety of measures of language including naming and picture description. We will contrast performance before and after tDCS using customary statistical techniques (e.g., ANOVA, t-test, etc). We will also perform analyses of MRI data from participants to determine if there is a correlation between measures such as blood flow and atrophy and improvement from tDCS.

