[name], Vyas, & Olson, 2013). tDCS has been used in the treatment of patients with neurodegenerative diseases (e.g., Benninger et al., 2010; Boggio et al., 2012; Hansen, 2012). We are aware of only one report in which tDCS was administered to a subject with PPA; there was significant improvement in some language functions in the absence of adverse effects (Wang, Wu, Chen, Yuan, & Zhang, 2013). HD-tDCS is an emerging technique of noninvasive brain stimulation that has been tested in a limited number of aphasic populations with comparable effects to traditional tDCS (Sebastian, Tsapkini & Tippett, 2016; Richardson et al., 2015). This new type of stimulation will provide a more focal flow of current than traditional tDCS. Primary progressive aphasia (PPA) is a behavioral disturbance characterized by the insidious onset and slow progression of language impairments in the context of a neurodegenerative disease. In different patients, the deficits may differentially impact comprehension, semantics or verbal fluency. Autopsy studies demonstrate that most patients with PPA suffer from Fronto-temporal dementia but Alzheimer's Disease, Dementia with Lewy Bodies and cortico-basal ganglionic degeneration may also cause the disorder. The disorder leads to a profound impairment in language and, ultimately, to a generalized severe dementia involving all domains of cognition. CILT is an intensive language therapy protocol, first developed by Pulvermuller and colleagues (2001) for use in language rehabilitation following stroke. The central principles of CILT are massed practice over many hours, combined with restricting communication to use of verbal language only (i.e., no gestures or other communication). Throughout the course of a CILT treatment, the difficulty of each stage of therapy is also scaled to individual patient performance, such that patients' language abilities can be sequentially behaviorally "shaped" to ensure a low rate of failure and a gradual increase of difficulty as improvements are made and new skills are retained. Traditional speech therapies are not typically as beneficial for individuals with PPA relative to individuals with post-stroke aphasia due to the progressive nature of the disorder. However, because the central principles of CILT involve massed practice over many hours, paired with constraining communication to the use of language, CILT may thus be useful in the *retention* of language in PPA in addition to aiding in the reacquisition of language after stroke. A recent study has shown modest benefits of an intensive CILT protocol in two individuals with PPA (Hameister et al., 2016), but further questions remain regarding how effective CILT may be for PPA and how long patients can expect the benefits of CILT to last.

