members of a specific category; semantic categories will include tools, animals, and vegetables. Subjects will also be asked to generate words starting with the letters F, A and S. - Repetition, Reading and Writing (single words) will be assessed using the materials developed by the NACC-FTD consortium; subjects are asked to read, write and repeat a series of words controlled for variables known to influence performance such as length, part of speech (noun, verb), imageability (desk vs. fate), age of acquisition, etc. - Elicited Speech Production: Speech samples will be elicited from subjects by presenting a picture book (e.g., Frog story) or scene to be described (Cookie Theft picture from the Boston Diagnostic Aphasia Examination) and asking subjects to describe what they see. Speech production will be scored off-line with respect to fluency (words/minute), grammatically well-formed sentences, mean length of utterance, nouns/100 words, verbs/100 words, phonemic errors, and phonetic errors. Half of subjects will undergo 10 sessions of sham stimulation first and will then undergo 10 sessions of real tDCS stimulation. Half of subjects will undergo 10 sessions of real tDCS stimulation first and will then undergo 10 sessions of sham stimulation. A complete language assessment will be performed before stimulation sessions, after the 10th stimulation session, and 6 and 12 weeks ( $\pm$  1 week) after the completion of stimulation sessions. Real tDCS stimulation will be administered using our standard apparatus (Magstim Eldith with 5x5 cm electrodes) using a current of 1.5 mA. (As a frame of reference, we routinely use 2 mA current in other studies.) The anode will be placed over the left fronto-temporal region of the brain and the cathode over the left occipito-parietal region. During sham stimulation, a 1.5 mA current will be delivered for approximately 10 seconds at the beginning of the sham condition before being extinguished over the course of seconds. As there is some evidence that engaging in the activity that one wishes to enhance while undergoing tDCS improves outcome, all subjects will be shown a children's picture book (e.g., the illustrated version of Cinderella) during the 20 minute period of stimulation and asked to narrate the story, regardless of whether they are in real tDCS stimulation or sham stimulation. Participants assigned to receive sham treatment first will cross over to real tDCS treatment after the 12-week follow up session. Each participant will then receive real tDCS stimulation for 10 sessions over the course of two weeks. The stimulation parameters and testing during treatment will be identical to the previous stimulation sessions, except this time participants will receive real tDCS stimulation instead of sham stimulation. Participants assigned to receive real tDCS stimulation first will cross over to sham stimulation after the 12-week follow up session. Each participant will then receive sham stimulation for 10 sessions over the course of two weeks. The stimulation parameters and language testing during treatment will be identical to the previous stimulation sessions, except this time participants will receive sham stimulation instead of real tDCS

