### ***2.2 Potential Study Benefits of HD-tDCS+CILT Sub-study***

The study is being performed to determine if HD-tDCS in combination with CILT improves subjects' language performance. The potential benefit of the study to the subjects, therefore, is that they will improve with respect to language function. This may occur during CILT+sham, CILT+HD-tDCS, or both. The study will also be of benefit to the community of physicians and clinicians attempting to treat PPA.

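### The trial is a sham-controlled cross-over, but neither general statement of the efficacy analysis specifies an active-versus-sham comparison

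*Combined protocol and SAP*

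**What the plan says.** **Design.** Section 2.1, Design of tDCS-Only Study, states: "This is a sham-controlled, full cross-over study design". The HD-tDCS+CILT sub-study takes over that design with two exceptions, an extra baseline session and an optional booster round. The svPPA sub-study is also a sham-controlled cross-over; its design section describes the assignment once as pseudo-random and once as random. In each part half the participants have sham first and half have active first, and the 12-week visit of the first block is the baseline of the second.

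**Analysis.** There are two general statements of the efficacy analysis.
- Objectives, section 2, Primary Outcome Variable(s): "We will contrast performance before and after tDCS using customary statistical techniques".
- Study Procedures, section 2, Statistical Analysis: within each subject, "change in performance from the baseline testing session to the post-therapy (0, 6, 12 weeks post tDCS) will be compared using t-tests". Analysis of variance and similar methods are listed as well. The section adds: "Depending on our ability to recruit a reasonable sample, group analyses will be also be performed".

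Neither mentions sham, an active-minus-sham contrast, period, sequence or carry-over. No sub-study has an analysis section of its own.

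**Aim.** The Protocol Abstract says of the HD sub-study that "we will investigate whether HD-tDCS can enhance the potential benefits of speech therapy". That implies a comparison with sham, but it is an aim and not an analysis.

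**The concern.** Change from baseline during an active block mixes any tDCS effect with everything else that happens in those weeks. The documents themselves point to such change in both directions.

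- **Upward.** Language activity runs in both conditions. In tDCS-Only, participants are "asked to narrate the story, regardless of whether they are in real tDCS stimulation or sham stimulation". The HD sub-study gives CILT and the svPPA sub-study gives word training, each under active and sham alike. On improvement in the HD sub-study, the benefits section says: "This may occur during CILT+sham, CILT+HD-tDCS, or both".
- **Downward.** The Background describes PPA as having "insidious onset and slow progression of language impairments in the context of a neurodegenerative disease".

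The sham block is what separates these influences from tDCS. If the analysis is carried out as the Primary Outcome section words it, a gain that sham produces equally is credited to tDCS, or background decline hides a real benefit, and the ten sham sessions contribute nothing to the efficacy result. If the Statistical Analysis section is read more generously, the comparator, the time point (three are offered) and the model are still open and could be settled after the data are seen.

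**Working it through.** **Step 1. Text against design.** The plan states no alpha, power, SD, effect size or calculated sample size, so there is no figure to reproduce. Of the two general analysis statements, none names sham. Of the three parts, all have a sham block with its own pre-stimulation baseline. The data for an active-minus-sham contrast are therefore collected, but the contrast is not specified.

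**Step 2. False positives of a before/after test (illustration).** Inputs: n = 10 per year × 2 years = 20 (sections 3.1 and 3.2, Study Duration; no figure is given for svPPA). Assumed: a group one-sample t-test, two-sided 5%, no tDCS effect, and a non-specific gain d in SDs of the change score. The rejection probability is P(|T| > t(0.975, n−1)), with T noncentral t on n−1 degrees of freedom and noncentrality d√n. The critical value is 2.093 at n = 20 and 2.262 at n = 10.

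| d | d√20 | n = 20 | d√10 | n = 10 |
|---|---|---|---|---|
| 0.2 | 0.894 | 13.6% | 0.632 | 8.8% |
| 0.3 | 1.342 | 24.7% | 0.949 | 13.6% |
| 0.5 | 2.236 | 56.4% | 1.581 | 29.3% |

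A paired test of active change minus sham change, simulated 100,000 times per setting with shared shifts of 0 to 0.8 SD and no period or carry-over effect, rejected 4.9% to 5.1% of the time at both sample sizes.

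**Step 3. Masked benefit (illustration).** Take a true benefit of 0.5 SD, n = 20, and a background decline of 0, 0.2, 0.3 or 0.5 SD. The net shift is 0.5, 0.3, 0.2 or 0. The before/after test shows a significant benefit 56.4%, 24.6%, 13.3% or 2.5% of the time.

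**Step 4. Price of the proper contrast.** Assume change SD 1, 10 per sequence, complete data and between-block correlation ρ. The period-adjusted active-minus-sham estimate has SE = √(2(1−ρ)/20) on 18 degrees of freedom.

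| ρ | SE | Power at 0.5 SD | Effect for 80% power |
|---|---|---|---|
| −0.2 | 0.346 | 28% | 1.03 SD |
| 0 | 0.316 | 32% | 0.94 SD |
| 0.3 | 0.265 | 43% | 0.78 SD |

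A comparison using block 1 only has SE = √(1/10 + 1/10) = 0.447 and needs 1.32 SD for 80% power.

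**Step 5. Two points the fix must cover.**
- *Carry-over.* Suppose the true benefit is 0.50 SD, half of it remains at the block 2 baseline, and that half fades during the sham block. In the active-first sequence the sham change is −0.25, so the contrast is 0.50 + 0.25 = 0.75. In the sham-first sequence it is 0.50. The average is (0.75 + 0.50)/2 = 0.625, not 0.50.
- *Missing second block.* In simulations with assumed cut-offs for stopping on worsening and zero between-block correlation, analysing only participants with both blocks shrank a true 0.50 SD to about 0.37 to 0.46 SD.

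**The case against.** The strongest reply is that the Statistical Analysis section is terse and not wrong. It says that changes will be compared in a within-subject design. Comparing changes needs two per person, the design supplies exactly two, and the Abstract states a comparative aim. This is a fair reading, and it rules out one inference a reader might draw, namely that the investigators plan to ignore sham. The documents do not say that. They leave the contrast unstated in one place and word it as before against after in the other. Even on the generous reading, the comparator, time point and model are missing.

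A second reply is that the percentages are not those of the planned analysis. That stands in part. The section analyses each subject's data and makes group tests conditional, and the shifts, SDs and alpha above are assumptions. The figures show the direction of the error and how it grows. They do not give the trial's actual error rate.

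Two limits of scope also stand. The svPPA part should not be called simply randomised, since its own section uses both terms. Its procedures also describe item-level comparisons for generalisation of training, so the two statements are the only general ones, not the only ones of any kind; those item comparisons do not name sham either.

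**Conclusion.** The concern holds as a gap in specification with a real consequence, and it should be closed before any analysis. Neither general analysis statement uses the control that all three parts are built around. Followed as worded, a before/after analysis cannot isolate a tDCS effect and can mislead in either direction.

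The size is illustrative: 14%, 25% or 56% false positives for a shared gain of 0.2, 0.3 or 0.5 SD at n = 20, and a true 0.5 SD benefit detected as little as 2.5% of the time if an equal decline runs alongside it. These figures rest on a group t-test at two-sided 5%, about 20 participants, and shifts that the documents neither give nor exclude. A reader might take them as the plan's false-positive rate. The documents do not support that, because they fix neither the test nor the shift, and an active-versus-sham comparison may be what is meant.

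**What to change.** Replace the first sentence of section 2, Statistical Analysis, and align section 2, Primary Outcome Variable(s), with:

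> The primary analysis, done whatever the sample size, compares active with sham. For each of the two assigned blocks, change in the primary measure is taken from that block's own pre-stimulation baseline to the assessment after the tenth session. The active-minus-sham difference is estimated with treatment and period in the model, keeping participants who have only one block, and is reported with its 95% confidence interval. The optional booster block is excluded. Because the block 2 baseline is the block 1 12-week visit, carry-over is examined by comparing the block 2 baseline with the block 1 baseline by sequence, and by a block-1-only comparison as a sensitivity analysis. Participants without both blocks are listed with reasons. Contrasts at the later visits that each part schedules are secondary. Changes within one condition and single-subject analyses are descriptive.

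The detailed mixed-model settings can be left to the trial statistician. Week 1 values should not stand in for the change after the tenth session in the primary analysis, because that mixes time points. The carry-over checks will be imprecise at this sample size, so an unremarkable result should not be reported as proof of no carry-over.

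Two matters need reconciling separately:
- On significant worsening, Procedures 1.1 and 1.3 say that the study is discontinued, while Procedures 1.2 says that the participant's visits are. The analysis text should not settle which is meant.
- The elicited-speech endpoint in the Statistical Analysis section does not appear in the baseline test lists of Procedures 1.2 and 1.3.

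**Cost.** Analysis wording only, with no new visits. The contrast is noisier than before/after: with 20 participants and complete data it needs about 0.8 to 1.0 SD for 80% power (ρ from 0.3 to −0.2), so the result may look less favourable.
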